6.2 Technical Factors

- 6.2.1 RT will be delivered with megavoltage equipment at energies ≥ 6 MV. Any FDA cleared external beam radiation delivery system may be used (including conventional linear accelerators). All treatment fractions (as specified above in Table 1) will be delivered on consecutive treatment days. All patients will be positioned via a combination of rigid immobilization and daily image guidance to ensure positioning accuracy of 3 mm or better, and of a magnitude that justifies the PTV margin applied (the treating radiation oncologist must document the immobilization and localization methods applied).

6.3 EBRT Localization, Simulation, and Immobilization

- 6.3.1 Simulation will be CT- and/or MRI-based (if available) in all cases. The use of contrast at the time of simulation is not required. Participants will be positioned on a flat tabletop with a customized immobilization for stabilization and setup reproducibility, with the patient in the same position and immobilization device as for treatment. CT images should be acquired at a slice thickness of ≤ 3 mm. Target volumes (Section 6.4.1) and normal critical structures (Section 6.4.1.5) will be defined in the slices in which they are visualized.

6.4 Treatment Planning/Target Volumes

- 6.4.1 The definition of volumes will be in accordance with the ICRU Report #50: Prescribing, Recording, and Reporting Photon Beam Therapy.

- 6.4.1.1 The Gross Tumor Volume (GTV) is defined will be defined using a CT and/or contrast-enhanced MRI (obtained prior to the initiation of re-irradiation). If no residual enhancing tumor is noted, the post-operative resection cavity will be outlined.
- 6.4.1.2 The Clinical Target Volume (CTV) is the GTV plus areas considered to contain microscopic disease. A CTV expansion of no more than 5 mm is optional for lesions measuring less than 3.5 cm in maximum diameter or if this is a new lesion, but must be reported when used. Otherwise, no CTV expansion is expressly recommended.
- 6.4.1.3 The Planning Target Volume (PTV) will provide a margin around the CTV to compensate for the variability of treatment set up and internal organ motion. A range of 1-5 mm around the CTV is required to define each respective PTV. As noted above in Section 6.3.1, daily image guidance to ensure positioning accuracy of 3 mm or better.
- 6.4.1.4 The ICRU Reference Points are to be located in the central part of the PTV and, secondly, on or near the central axis of the beams. Typically these points should be located on the beam axes or at the intersection of the beam axes.
- 6.4.1.5 The PTV forms the entire target as described. 3D-conformal, intensity modulated radiation therapy (IMRT), Volumetric Arc Therapy (VMAT), and/or fractionated stereotactic radiotherapy (SRT) are all acceptable modalities of radiation treatment delivery. If IMRT or SRT are intended, to avoid delays resulting from unplanned equipment availability, photon therapy may be administered using 3D-conformal radiotherapy at the discretion of the treating radiation oncologist.

6.5 Critical Structures

Critical structure dose constraints shall remain consistent with Tables 7-9 above. While every effort should be made to deliver prescription doses to the PTV as specified while adhering to these constraints, it is recognized that certain anatomical factors may prevent this.

For purposes of compliance, up to a 5% absolute increase in the volume of critical structure receiving greater than the specified dose will be considered “variation acceptable,” without a protocol deviation. Any increase in critical structure volume greater than 5% receiving more than the specified dose will be considered a “deviation unacceptable.” It is at this point that a dose reduction should be considered.

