		minimum doses < 80% of the prescription dose are permissible if they occur at an area of overlap with an organ at risk (OAR)	minimum doses < 80% of the prescription dose are unacceptable if they do not occur at an area of overlap with an OAR
Maximum dose to the PTV (0.03 cc)	≤ 120% of the prescription dose (44.06 Gy)	≤ 130% of the prescription dose (47.74 Gy)	> 130% of the prescription dose (47.74 Gy)

6.1.3 Normal Tissue Constraints: Participants shall receive prescription doses to the PTV (with the above constraints). All attempts should be made to deliver the PTV dose with the above heterogeneity constraints with adherence to critical structure dose constraints. The normal tissue dose constraints are designed to be equivalent in terms of biologically effective dose (BED), to those used in the RTOG 1205 trial. The BED is defined as:

$$BED_{\alpha/\beta} = nd \left(1 + \frac{d}{\alpha/\beta} \right)$$

where n is the number of fractions and d is the dose per fraction. For central nervous system toxicity an alpha/beta ratio of 2 was used. The MARS-Glio dose constraints for the two phases combined in BED with an alpha/beta ratio of 2 are thus given by

$$C_{MARS-Glio,total,BED} = C_{RTOG\ 1205,AD} \left(1 + \frac{C_{RTOG\ 1205,AD}/10}{2} \right)$$

where $C_{RTOG\ 1205,AD}$ is the RTOG 1205 absorbed dose. For the individual phases the dose constraints, in absorbed doses, are given by

$$C_{MARS-Glio,phase\ x,AD} = n_{phase\ x} \left(-1 + \sqrt{1 + \frac{4C_{MARS-Glio,total,BED} \frac{BED_{\alpha/\beta,phase\ x}}{BED_{\alpha/\beta,total}}}{n_{phase\ x} \alpha/\beta}} \right) / 2 / \alpha/\beta$$

$$BED_{2,phase\ 1} = 7 \times 3.96 \left(1 + \frac{3.96}{2} \right) = 82.61\ Gy_2$$

$$BED_{2,phase\ 2} = 9 \times 1.00 \left(1 + \frac{1.00}{2} \right) = 13.50\ Gy_2$$

$$BED_{2,total} = BED_{2,phase\ 1} + BED_{2,phase\ 2} = 96.11\ Gy_2$$

$$\frac{BED_{2,phase\ 1}}{BED_{2,total}} = \frac{82.61}{96.11} = 0.861$$

$$\frac{BED_{2,phase\ 2}}{BED_{2,total}} = \frac{13.50}{96.11} = 0.140$$

$$C_{MARS-Glio,phase\ 1,AD} = 7 \left(-1 + \sqrt{1 + \frac{4C_{MARS-Glio,total,BED} \times 0.861}{7 \times 2}} \right)$$

$$C_{MARS-Glio,phase 2,AD} = 9 \left(-1 + \sqrt{1 + \frac{4C_{MARS-Glio,total,BED} \times 0.140}{9 \times 2}} \right)$$

The dose constraints for the RTOG 1205 trial, in absorbed dose, are displayed in Table 6.

Table 6. RTOG 1205 Normal Tissue Dose Constraints (given as absorbed dose)

Dose Metric	Per Protocol	Variation Acceptable	Deviation Unacceptable

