Scenario (1): Previous radiation to the local area including critical organs at risk			
Maximum Dose to PRV for Optic Nerves and Chiasm (D _{0.03 cc})	Less than or equal to 20.00 Gy	Greater than 20.00 Gy but less than or equal to 25.00 Gy	Greater than 25.00 Gy
Maximum Dose to Brainstem (0.03 cc)	Less than or equal to 24.00 Gy	Greater than 24.00 Gy but less than or equal to 30.00 Gy	Greater than 30.00 Gy
Scenario (2): No previous radiation to the local area or critical organs at risk			
Maximum Dose to PRV for Optic Nerves and Chiasm (0.03 cc)	Less than or equal to 35.00 Gy (the prescription dose)	Greater than 35.00 Gy but less than or equal to 36.75 Gy (105 % of the prescription dose)	Greater than 36.75 Gy (105% of the prescription dose)
Maximum Dose to Brainstem (0.03 cc)	Less than or equal to 35.00 Gy (the prescription dose)	Greater than 35.00 Gy but less than or equal to 36.75 Gy (105 % of the prescription dose)	Greater than 36.75 Gy (105 % of the prescription dose)

Table 7 shows the dose constraints for the combined phases in BED with an alpha/beta ratio of 2 for the optic nerves, optic chiasm and brainstem (BED₂).

Table 7. MARS-Glio phases 1 and 2 combined normal tissue dose constraints (given as BED with an alpha/beta ratio of 2)

Dose Metric	Per Protocol	Variation Acceptable	Deviation Unacceptable
Scenario (1): Previous radiation to the local area including critical organs at risk			
Maximum Dose to PRV for Optic Nerves and Chiasm (D _{0.03 cc})	Less than or equal to 40.00 Gy ₂	Greater than 40.00 Gy ₂ but less than or equal to 56.25 Gy ₂	Greater than 56.25 Gy ₂
Maximum Dose to Brainstem (0.03 cc)	Less than or equal to 52.80	Greater than 52.80 Gy ₂ but less than or equal	Greater than 75.00 Gy ₂

	Gy ₂	to 75.00 Gy ₂	
Scenario (2): No previous radiation to the local area or critical organs at risk			
Maximum Dose to PRV for Optic Nerves and Chiasm (0.03 cc)	Less than or equal to 96.11 Gy ₂ (the prescription dose)	Greater than 96.11 Gy ₂ but less than or equal to 104.28 Gy ₂	Greater than 104.28 Gy ₂
Maximum Dose to Brainstem (0.03 cc)	Less than or equal to 96.11 Gy ₂ (the prescription dose)	Greater than 96.11 Gy ₂ but less than or equal to 104.28 Gy ₂	Greater than 104.28 Gy ₂

Tables 8 and 9 give the phase 1 and phase 2 normal tissue dose constraints in absorbed doses, respectively.

Table 8. MARS-Glio phase 1 normal tissue dose constraints (given as absorbed dose)

Dose Metric	Per Protocol	Variation Acceptable	Deviation Unacceptable

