Scenario (1): Previous radiation to the local area including critical organs at risk			
Maximum Dose to PRV for Optic Nerves and Chiasm (D _{0.03 cc})	Less than or equal to 16.05 Gy	Greater than 16.05 Gy but less than or equal to 19.96 Gy	Greater than 19.96 Gy
Maximum Dose to Brainstem (0.03 cc)	Less than or equal to 19.18 Gy	Greater than 19.18 Gy but less than or equal to 23.87 Gy	Greater than 23.87 Gy
Scenario (2): No previous radiation to the local area or critical organs at risk			
Maximum Dose to PRV for Optic Nerves and Chiasm (0.03 cc)	Less than or equal to 27.75 Gy	Greater than 27.75 Gy but less than or equal to 29.14 Gy	Greater than 29.14 Gy
Maximum Dose to Brainstem (0.03 cc)	Less than or equal to 27.75 Gy	Greater than 27.75 Gy but less than or equal to 29.14 Gy	Greater than 29.14 Gy

Table 9. MARS-Glio phase 2 normal tissue dose constraints (given as absorbed dose)

Dose Metric	Per Protocol	Variation Acceptable	Deviation Unacceptable
Scenario (1): Previous radiation to the local area including critical organs at risk			
Maximum Dose to	Less than or	Greater than 4.48 Gy	Greater than 5.93

PRV for Optic Nerves and Chiasm (D _{0.03 cc})	equal to 4.48 Gy	but less than or equal to 5.93 Gy	Gy
Maximum Dose to Brainstem (0.03 cc)	Less than or equal to 5.63 Gy	Greater than 5.63 Gy but less than or equal to 7.43 Gy	Greater than 7.43 Gy
Scenario (2): No previous radiation to the local area or critical organs at risk			
Maximum Dose to PRV for Optic Nerves and Chiasm (0.03 cc)	Less than or equal to 8.98 Gy	Greater than 8.98 Gy but less than or equal to 9.54 Gy	Greater than 9.54 Gy
Maximum Dose to Brainstem (0.03 cc)	Less than or equal to 8.98 Gy	Greater than 8.98 Gy but less than or equal to 9.54 Gy	Greater than 9.54 Gy

See Section 6.5 below for specifics regarding when to implement a dose reduction. The final prescription dose will be reported specifically to the study coordinator and recorded on a patient-by-patient basis.

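### Section 6.5 and Tables 7–9 grade the same organ dose by incompatible rules under the same labels, so the dose-reduction trigger is inconsistent

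*Combined protocol and SAP*

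**What the plan says.** Section 6.1.3 sets the organ limits. "The normal tissue dose constraints are designed to be equivalent in terms of biologically effective dose (BED") to the RTOG 1205 limits. Every row of Tables 7–9 is a maximum dose to 0.03 cc, in three bands: per protocol, *variation acceptable* up to an upper dose, and *deviation unacceptable* above it. Where the organ has been irradiated before (Scenario 1), the last band in Table 7 begins at "Greater than 56.25" Gy₂ for the optic PRV and "Greater than 75.00" Gy₂ for the brainstem. After Table 9 the reader is sent on: "See Section 6.5 below for specifics regarding when to implement a dose reduction".

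Section 6.5 opens by affirming the tables: "Critical structure dose constraints shall remain consistent with Tables 7-9 above". It accepts that anatomy may prevent adherence, then gives its own compliance rule. First, "up to a 5% absolute increase in the volume of critical structure receiving greater than the specified dose will be considered" *variation acceptable*, without counting as a protocol deviation. Second, "Any increase in critical structure volume greater than 5% receiving more than the specified dose will be considered a" *deviation unacceptable*. It then adds: "It is at this point that a dose reduction should be considered".

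Section 6.6.3 cites Table 2 for target compliance and Table 3 for normal tissue compliance. Both are target coverage tables.

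**The concern.** The two rules share labels but measure different things. The tables ask how high the dose is in the hottest 0.03 cc. Section 6.5 asks what share of the structure lies above a dose that it does not identify; it could be the per-protocol limit or the ceiling. It puts no upper dose on the tolerated 5%, and no order of precedence is stated. Tables 7–9 contain no volume-based limit to which the 5% could apply instead.

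Because Section 6.1.3 hands the dose-reduction decision to Section 6.5, the answer matters for patients. In the looser direction, a small volume of optic structure or brainstem that has already been irradiated can exceed the Table 7 ceiling, be scored as no deviation, and not reach the stated point for considering a lower dose. The situation is foreseeable: exclusion 3.2.3 removes only tumors with extensive contact or involvement, and Tables 3–5 make explicit allowance for PTV–organ overlap.

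**Working it through.** **1. Reproducing the tables.** Inputs are the RTOG 1205 doses in Table 6 and α/β = 2 (Section 6.1.3). With 10 fractions, BED₂ = D(1 + D/20).

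- 24 Gy: 24 × 2.20 = 52.80
- 25 Gy: 25 × 2.25 = 56.25
- 30 Gy: 30 × 2.50 = 75.00

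These match Table 7. The phase limits follow from n(−1 + √(1 + 4·BED·f/(2n))), with n = 7, f = 0.861 and n = 9, f = 0.140. The Scenario 1 ceilings come out at 23.87 and 7.43 Gy (brainstem) and 19.96 and 5.92 Gy (optic). They agree with Tables 8–9 within 0.01 Gy.

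**2. When 5% is more than 0.03 cc.** 0.05 × V > 0.03 cc when V > 0.03/0.05 = 0.6 cc. Organ volumes are not in the documents; the following are assumptions.

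- Brainstem 20–40 cc: 5% is 1.0–2.0 cc, or 33–67 times 0.03 cc.
- Optic PRV 1–10 cc: 5% is 0.05–0.5 cc, or 1.7–17 times.

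**3. The grades side by side.** Reading A takes the specified dose as the per-protocol limit; reading B takes it as the ceiling.

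| Dose pattern | Tables 7–9 | 6.5, reading A | 6.5, reading B |
|---|---|---|---|
| Maximum between the two limits, ≤5% over the per-protocol limit | acceptable | acceptable | nothing over |
| Maximum between the two limits, >5% over the per-protocol limit | acceptable | **unacceptable** | nothing over |
| >0.03 cc over the ceiling, ≤5% over the specified dose | unacceptable | **acceptable** | **acceptable** |
| >5% over the ceiling | unacceptable | unacceptable | unacceptable |

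The third row is a clash on either reading; the second is a clash on reading A only.

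Examples, taking a 25 cc brainstem in Scenario 1:

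- 1.0 cc (4%) at 80 Gy₂ and the rest within 52.80 Gy₂ is unacceptable in Table 7, because 80 > 75.00, but acceptable in Section 6.5.
- 2.0 cc (8%) between 52.80 and 75.00 Gy₂ and none above is acceptable in Table 7 but unacceptable in Section 6.5 under reading A.

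**4. How far over the ceiling.** For phase doses D₁ and D₂, BED₂ = D₁(1 + D₁/14) + D₂(1 + D₂/18).

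- Full prescription (27.72 and 9.00 Gy): 82.61 + 13.50 = 96.11 Gy₂. This is 96.11/56.25 = 171% of the optic ceiling and 96.11/75.00 = 128% of the brainstem ceiling.
- 80% PTV floor in Tables 3–4 (22.18 and 7.20 Gy): 57.32 + 10.08 = 67.40 Gy₂. This is 67.40/56.25 = 120% of the optic ceiling, but below the brainstem ceiling of 75.00. By phase the result is the same: 22.18 < 23.87 and 7.20 < 7.43 Gy for the brainstem, 22.18 > 19.96 and 7.20 > 5.93 Gy for the optic PRV.

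**5. A trap for the remedy.** In Scenario 2 an organ at exactly the prescription is per protocol in Table 7 (96.11 Gy₂) and Table 8 (27.72 ≤ 27.75 Gy). Table 9 sets 8.98 Gy, below the 9.00 Gy phase 2 prescription, and so grades it one step lower.

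**The case against.** The best defense is that Section 6.5 begins by keeping Tables 7–9 in force and asks for every effort to meet them. The 5% can then be read as a scoring tolerance for difficult anatomy. Dose reduction is only to be considered, so nothing forbids it earlier, and Section 6.6.2 provides ongoing quality review by the study chair. This limits the likely harm. It does not reconcile the text: one plan cannot be both free of a deviation and an unacceptable deviation.

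Three stronger inferences are tempting and are not supported.

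- *That Section 6.5 is always the looser rule.* Under reading A it can also be stricter.
- *That it forces planners to overdose an organ, or licenses planning to full dose.* Tables 3–5 allow the PTV minimum to fall below 80% where it overlaps an organ, so the ceilings can be respected. Without that exception, the squeeze at the 80% floor is confined to the optic PRV in Scenario 1.
- *That equivalence with RTOG 1205 is lost.* The limit values remain equivalent; what is unclear is how exceeding them is graded. Whether RTOG 1205 had a volume tolerance cannot be seen from these documents.

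A hot-spot figure of 129.56 Gy₂ can be obtained from the 120% PTV maxima (33.26 and 10.80 Gy). Those are themselves 0.03 cc maxima and would have to coincide inside the organ in both phases, so they do not describe 5% of a structure.

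The tables refer to a PRV for the optic structures and Section 6.5 to the critical structure, and the baseline for the absolute increase is not given. If the 5% applies to a structure of 0.6 cc or less, the looser clash disappears for it.

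**Conclusion.** The contradiction stands, as an inconsistent grading rule and dose-reduction trigger that can err in either direction. The looser direction is the one with a safety consequence: more than 0.03 cc, and up to 5%, of a previously irradiated optic structure or brainstem can exceed the Table 7 ceiling without a deviation being recorded. The 0.6 cc threshold and the BED figures rest only on the protocol's numbers; the tolerated volumes in cc rest on assumed organ sizes.

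The importance is moderate. The documents give no basis for counting affected patients, and there may be few among 14. The primary endpoint is defined by receipt and timing of fractions, so the 13-of-14 feasibility rule is not affected. The change should be made because it is cheap and concerns re-irradiated critical organs.

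**What to change.** In Section 6.5:

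- State that the 0.03 cc ceilings in Tables 7–9 always apply, and that exceeding one is *deviation unacceptable* and triggers consideration of dose reduction.
- Either delete the 5% tolerance, or keep it with the specified dose defined as the per-protocol limit, the structure named (organ or PRV), and its use confined to doses at or below the ceiling. If it is kept, note in the tables that the middle band holds only up to 5% of the volume; otherwise the reverse clash remains.
- Say which table governs when they differ, for example Table 7 combined BED for the final grade, with Tables 8–9 as per-phase planning limits. The alternative is to set the Scenario 2 per-protocol limit in Table 9 to 9.00 Gy. A rule that the worst grade counts, with all values unchanged, should not be adopted: it would downgrade a Scenario 2 organ at exact prescription.

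In Section 6.6.3, cite Tables 3–5 for target and Tables 7–9 for normal tissue.

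The cost is wording in two sections and, only under the alternative, the Scenario 2 entries of Table 9. Any plan already accepted under the 5% tolerance needs re-scoring. Some targets touching an organ will be underdosed at the overlap, which Tables 3–5 already permit. Sample size and the primary analysis do not change.

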6.6 Quality Assurance

6.6.1 Documentation Requirements

The institution will archive treatment prescription and verification images for later review by the study chair if requested. At least one port film or pretreatment alignment film per

field along with the digital reconstructed radiographs (DRRs) from the treatment planning program or, alternatively, a simulation verification radiograph shall be acquired and kept for evaluation if requested except where geometrically impractical.

6.6.2 Radiation Quality Assurance Reviews

The study chair will oversee quality assurance reviews for patients treated on this study. RT quality assurance reviews will be ongoing and performed remotely. RT quality assurance reviews will be facilitated by study chair.

6.6.3 Compliance Criteria

Cases that meet criteria as stated in Section 6.1.1 will be scored as per protocol. See Table 2 and Table 3 for target and normal tissue compliance criteria respectively.

6.7 Radiation Adverse Events

All participants will be seen weekly by their treating radiation oncologist while undergoing therapy. Any observations with respect to symptoms/side effects that are possibly, probably, or definitely related to recurrent glioblastoma or irradiation to the brain will be followed for adverse event (AE) reporting.

Clinical discretion may be used in managing radiotherapy-related side effects.

6.8 Radiation Adverse Event Reporting

Any observations with respect to symptoms/side effects that are possibly, probably, or definitely related to recurrent glioblastoma or irradiation to the brain will be followed for AE reporting. See Section 9 for listing of particular AEs that will be monitored. This is not an all-inclusive list, and any AE that is considered by the treating physician to be related to recurrent glioblastoma and/or irradiation to the brain will be followed with attributions and grading according to CTCV 4.0. Routine solicited AEs not considered by treating physicians to be related to recurrent glioblastoma or irradiation to the brain will be treated according to institutional guidelines and managed by the patient's oncology team in the best clinical judgment of the responsible physician.

6.9 Criteria for Discontinuation of Protocol Disease progression

Unacceptable toxicity to the participant (at the discretion of the treating physician).
Reasons for removal must be clearly documented on the appropriate case report form/flowsheet.

The participant may withdraw from the study at any time for any reason.

If protocol treatment is discontinued, follow-up and data collection will continue as specified in the protocol

7. DRUG THERAPY

This protocol does not specify any investigational drug therapy. Participants receiving re-irradiation may not receive concurrent cytotoxic chemotherapy (i.e. temozolomide, CCNU, vincristine, procarbazine) or concurrent immunotherapy (i.e. pembrolizumab, nivolumab). Participants may receive sequential systemic therapy before or after radiation without limitation. Participants may receive concurrent corticosteroid and/or anti-angiogenic therapy (i.e. bevacizumab) if clinically indicated.

8. SURGERY

This protocol does not mandate neurosurgical resection prior to receipt of re-irradiation. Participants may undergo a planned neurosurgical resection prior to registration and receipt of re-irradiation at the discretion of the treatment multidisciplinary team. Such participants will be required to have recovered from the acute effects of neurosurgery prior to initiating re-irradiation at the judgment of the treating radiation oncologist. There is no maximum or minimum interval from the time of prior surgery to initiation of re-irradiation. If participants underwent a preceding neurosurgical resection, the target volume for re-irradiation will include the surgical cavity plus any residual enhancing disease.

9. ADVERSE EVENTS

Toxicity assessments will be performed using the active version of the NCI CTCAE which is available at: http://ctep.cancer.gov/protocoldevelopment/electronic_applications/ctc.htm

Grade 1-2 fatigue will be managed supportively. Activity will be encouraged.

Grade 3 fatigue can be managed per above, with the additional of low-dose dexamethasone and/or methylphenidate 2.5-5.0 mg daily, as needed.

Grade 1-2 nausea can be managed with as-needed antiemetics such as Zofran 8 mg prn, steroids (dexamethasone preferred, e.g. 2 mg PO BID), and hydration.

Grade 3 nausea can be managed per above with the addition of intravenous fluids and electrolyte repletion. Hospitalization and a treatment break can be considered.

Grade 1 headache can be managed with Tylenol 650 mg BID and consideration of low-dose dexamethasone (2 mg PO BID)

Grade 2 headache can be managed per above, with narcotics as needed.

Grade 3 headache can be managed per above, with consideration of high-dose dexamethasone (4 mg PO TID) and a treatment break.

Symptomatic edema can be managed with dexamethasone (2 mg PO BID) at discretion of treating physician.

Seizures will be managed with antiepileptic drugs, consideration of a treatment break, and referral to Neuro-oncology or admission, depending on the nature and severity of the episode.

Any observations with respect to symptoms or side effects that are possibly, probably, or definitely related to brain metastases or radiation to the brain will be followed for AE reporting.

